4.2 Inclusion and Exclusion Criteria

Inclusion Criteria

1. Men and women 16 – 70 years (at the time of enrollment; ± 2 years) of age previously enrolled in the Part 1 study and residing in the area of the study.
2. Participants must have at least 1 palpable subcutaneous nodule (onchocercoma).
3. Participants with baseline skin Mf counts ≥ 3 Mf/mg at the time of enrollment into the Part 1 study (Part I, see above).

Exclusion Criteria

1. Pregnant and breastfeeding mothers within 1 month of giving birth
2. Severe eye disease at baseline including uveitis, severe glaucoma, , severe keratitis, and/or cataracts that interfere with visualization of the posterior segment of the eye as well as the list of ocular diseases as outlined below Individuals who are excluded with significant ocular disease will be referred to appropriate ophthalmological care in a health facility (the district hospital) or the any other health facility in Ghana, where affected subjects will obtain appropriate care (University hospital or private ophthalmologist). All ocular disease exclusion criteria apply to either eye. Bilateral disease is not necessary to exclude a participant. A participant will be excluded if any of the criteria are met for one eye.
 - a. Any cataract of any type preventing clear visualization of fundus or imaging on Optical Coherence Tomography (OCT).
 - b. Severe retinal nerve fiber layer thinning in the superior and inferior quadrant analysis on Ocular Coherence Tomography of the optic nerve with a corresponding visual field defect of grade 2 or worse on the same eye.
 - i. If Ocular Coherence Tomography is not available, the following exclusion criteria will apply: vertical Cup/disc ratio on fundoscopy (not by OCT reading) greater than or equal to 0.80.
 - c. Intraocular pressure (IOP) greater than or equal to 25 by Goldmann tonometry.¹²
 - d. Retinal Detachment or Retinal Break
 - e. Acute ocular infection (i.e., Viral conjunctivitis, corneal ulcer, endophthalmitis)
 - f. Optic Atrophy with visual field defect reproducible on confrontation visual field testing..
 - g. Exam consistent with Herpes Simplex Virus eye infection
 - h. Homonymous hemianopsia, quadrantsopsia, bitemporal hemianopsia, or central scotoma related to cerebral vascular disease by Automated Visual Field testing and confrontation visual field testing.
 - i. Acute Angle Closure Glaucoma
 - j. Gonioscopy grade 0 (slit) limiting ability to safely dilate patient
 - k. Severe Tremor, blepharospasm, or other voluntary or involuntary motor condition that prevents ability to examine patient with slit lamp, OCT, gonioscopy, IOP measurement, fundus photography, and Frequency doubling technology perimetry.
 - l. Cognitive impairment sufficient to prevent ability to understand and perform Visual Acuity Test with Tumbling E chart, confrontation visual field, slit lamp exam, or any other ocular exam component.
 - m. Optic nerve edema
 - n. Active retinopathy or retinitis not attributable to onchocercal disease
 - o. History of uveitis not associated with onchocercal disease
 - p. Any pre-existing chorioretinal scar or retinal degeneration and other significant retinal pathologies (foveomacular schisis, dystrophies, arterial macroaneurysms etc) involving the macula.
 - q. Severe ocular pain, that patient rates as 9 or 10 out of 10 pain.
 - r. Best corrected or pinhole visual acuity worse than 6/60 (20/200)
 - s. Age related macular degeneration (AMD)
3. Significant comorbidities such as renal insufficiency, liver failure, or any other acute or chronic illness identified by study clinicians and investigators that interferes with the participant's ability to go to school or work or perform routine household chores.

4. Prior allergic / hypersensitivity reactions or intolerance to IVM, albendazole, or DEC.
5. Treatment with IVM outside of the study after the pre-treatment clearing dose provided in the Part I study.
6. >5 motile Mf in the anterior chamber in either eye at the time of enrollment (after pre-treatment with IVM).

Note: The cut-off of 5 Mf was suggested by external reviewers of our proposal to the Gates Foundation. These are experts in onchocerciasis selected by the Foundation. The reviews were anonymous, so we do not know their names. They also suggested that we exclude persons with any Mf in the posterior segment of the eye, and we have added that exclusion criteria that in the protocol.

7. Any Mf identified in the posterior segment of the eye at the time of enrollment (six months after pre-treatment with IVM).
8. Any other condition identified by study clinicians or investigators that may preclude participation in the study.

4.3 Participant Exclusion from Routine MDA

Participants will be informed that they should not participate in MDA distributed by the Ghana Health Service in their communities during this study period. Participants will receive a laminated card to identify them as participants in the study (Appendix A). Participants will present these cards to community drug distributors. Study investigators will communicate with local health officials responsible for MDA to inform them of the study and ensure that they are aware that there are study participants who should be excluded from routine MDA for the duration of the study.

4.4 Randomization

At least six months after treatment with ivermectin (-5.5 months or +12 months) in the preceding Part I trial, participants will first be split into two strata – those without ocular Mf detected six months after ivermectin pretreatment in the Part I preceding study *AND* without ocular Mf detected at baseline in the part II study will be in stratum 1. Those participants with ocular Mf detected 6 months after ivermectin pretreatment in the preceding study *OR* with ocular Mf detected at the baseline exam for this study will be in stratum 2. Stratum 1 will be enrolled first, followed by stratum 2. This is a safety precaution that will ensure that participants with *any* Mf in either eye 6 months after ivermectin pretreatment in the previous study will be the last to be dosed with combination drug treatments in this study. The decision to stratify so that persons who might be at higher risk are dosed last was based on recommendations from external expert reviewers of our grant proposal.

Members of each stratum will be evenly randomized into one of three treatment arms:

Stratum 1: Ocular Mf negative by slit lamp six months after ivermectin pretreatment (in Part I) AND ocular Mf negative by slit lamp at baseline enrollment

1. IVM + ALB - Single dose of oral IVM (150 µg/kg) plus ALB (400 mg) (IVM/ALB)
2. IDA x 1 dose - Single dose of oral IVM (150 µg/kg), DEC (6 mg/kg) and ALB (400 mg)
3. IDA x 3 doses -Once daily for 3 days oral IVM (150 µg/kg), DEC (6 mg/kg) and ALB (400 mg)

Stratum 2: Oular Mf positive 6 months after ivermectin pre-treatment (in Part I) **OR** ocular Mf positive at baseline enrollment (ocular Mf counts by slit lamp greater than 0 but < 5 in either eye)

1. IVM + ALB - Single dose of oral IVM (150 µg/kg) plus ALB (400 mg) (IVM/ALB)
2. IDA x 1 dose - Single dose of oral IVM (150 µg/kg), DEC (6 mg/kg) and ALB (400 mg)
3. IDA x 3 doses -Once daily for 3 days oral IVM (150 µg/kg), DEC (6 mg/kg) and ALB (400 mg)

4.5 Treatment masking

While this is an open label study and there is no placebo treatment group, all efforts will be made to ensure that that medical/technical staff assessing skin Mf, AEs and ophthalmological findings will be unaware of initial baseline skin and ocular Mf findings and treatment arm as best as possible.

This is especially important for those performing AE assessments and for persons reviewing nodule slides, because the primary objectives depend on those evaluations. A study pharmacist will be responsible for managing the randomization assignment list and treating patients accordingly. The pharmacist should be the only person at the study site who will know treatment assignments.

Treatment information will be kept separate from the rest of the participant case report form and shared only if required for medical purposes. Efforts will also be made to assure baseline infection status is not shared with examiners unless required for medical purposes in the case of severe or serious AEs.

The histologists reading the nodule histology slides will only be provided with histology slides identified by a patient number and nodule number. The histologist will have no other information about the patient.

Treatment and baseline infection status will be available to the study sponsor, data analysts, and DSMB. The data manager will un-mask the treatment assignment after the last participant has had their 3 month post-treatment evaluation. The safety data will then be compared by study arm. That will complete the safety study, which is separate from the efficacy study. Persons evaluating nodules will be masked regarding Mf counts and treatment assignment to avoid bias. Nodule data will be analyzed after the nodule evaluations have been completed. That part of the study is focused on the issue of whether IDA is superior to IVM and albendazole alone for killing or sterilizing adult worms.

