6 INSTRUCTIONS FOR SPECIMEN PREPARATION, HANDLING, AND STORAGE

6.1 Specimen and Sample Handling

Specimens will be tested in clinical laboratories at Kpassa (skin snips) and at the UHAS School of Public Health Research Centre in Hohoe, Ghana (blood, urine, skin snips). Onchocercal nodules will be fixed in preservative and processed for histology at a histology laboratory with CAP (College of American Pathologists) or an equivalent international certification.

Samples (serum, urine, skin snips, nodules) sent outside of Ghana for testing or storage will be completely de-identified (study ID number only). De-identified samples will be sent to Washington University in St. Louis and/or Case Western Reserve University (USA). Samples may be stored at one or more of these sites. These samples will be used for onchocerciasis related studies only.

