6.2 Specimen Shipment

Nodule histology slides will be read in two independent sites. One site will be the DOLF project reference laboratory ([name] Lab) at the Washington University in St. Louis. Shipments of nodules and slides will comply with Ghanaian and United States federal rules and with IATA regulations. The [name] Lab at Washington University in St. Louis is located at [name], [name]. Samples will be stored for up to 35 years and then destroyed according to regulatory guidance.

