11.6 Participant Privacy

Privacy of the study participants will be maintained by assigning a unique study identification number (UNID). All data, skin snip samples and results will be recorded and analyzed by UNID

with no personal identifiers. All information collected, including name, specific address, etc. that could identify subjects will be kept confidential and available only to the investigators and authorized study personnel.

All written forms (i.e., consent and any paper data collection forms) will be stored in a designated locked area with limited access. All forms will be labelled and filed in cabinets with the study protocol number, PI's names and collection dates. These cabinets will be metal and have functioning locks. Keys will be kept with the study site PI, Data Manager, or Study Coordinator. Any electronic devices used to enter or collect data will be password protected. PIs and/or Project Coordinator will authorize access. The paper forms will be stored for the duration of the study plus seven years per IRB protocol for primary data storage.

Data will be entered into an electronic data capture system (EDC) that is 21 CFR 11 compliant. No participant names will be collected in the EDC. The database will be password protected and the Principal Investigators will authorize access to the password. For data transfer outside of the EDC data files will be exported as transfer files and, to ensure confidentiality, all files will be encrypted and password protected.

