12.5 Financial Disclosure

The investigators listed in this protocol have no financial interests in the investigational products being researched in this study. This is an investigator-initiated study and the DOLF Project at Washington University in St. Louis Medical School is the sponsor of the study. The study is funded by a grant from the Bill and Melinda Gates Foundation. There is no financial agreement between the sponsor, funder, nor other investigators whereby the value of compensation would be influenced by the outcome of the study.

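### Nodule readers are promised masking, but slides carry the patient number, one of the two reading sites is the sponsor's laboratory, and no procedure prevents a slide being linked to its arm

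*Combined protocol and SAP*

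**What the plan says.** The trial is open label, and its primary efficacy endpoint is read from nodule sections (4.8). Section 4.5 stresses that masking matters most for adverse-event assessors and nodule readers, because the primary objectives depend on them. It commits to masking nodule readers to Mf counts and treatment. Its stated method is that histologists will "only be provided with histology slides identified by a patient number and nodule number", with nothing else about the patient.

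The same section sets the access rule: "Treatment and baseline infection status will be available to the study sponsor, data analysts, and DSMB". It also sets the timing: "The data manager will un-mask the treatment assignment after the last participant has had their 3 month post-treatment evaluation". At the study site, the pharmacist should be the only person who knows assignments.

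On who reads, section 6.2 says: "Nodule histology slides will be read in two independent sites". It adds: "One site will be the DOLF project reference laboratory". The second site is not named. Section 12.5 states that "the DOLF Project at Washington University in St. Louis Medical School is the sponsor of the study", and section 12.6 gives the sponsor's team a part in data management and statistical analysis.

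On identifiers, section 6.1 lets samples leave Ghana under the study ID number only, and section 11.6 says: "All data, skin snip samples and results will be recorded and analyzed by UNID".

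Section 4.8 provides two readers who do not see each other's results before entry, then reconcile together, with a third reader if they cannot agree. An APR immunostain helps to separate live from dead worms. Nodules are removed at 18 months (4.6).

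**The concern.** Whether a female worm is alive and carries embryos is a judgement made at the microscope. In an open-label trial, that judgement is protected if the reader cannot know the arm. Section 4.5 controls what is handed over with the slide. It does not control what the reader's own institution may already hold. The sponsor's organisation appears on both sides: it reads slides, and it has treatment status under the number written on them. Reading takes place after assignment has been unmasked.

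If a reader came to know the arm, even a modest one-sided drift in borderline calls would feed straight into the primary comparison. Nothing in the data would distinguish it from a drug effect.

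**Working it through.** **1. Does the slide label link to treatment?** Section 4.5 puts the patient number on the slide. Section 6.1 allows only the study ID on samples leaving Ghana. Section 11.6 records and analyses all data by that identifier. Taking the patient number to be the study ID (an inference, but the only identifier that 6.1 permits), anyone holding both a slide and the assignment list can join them. No slide-specific code is described.

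**2. Who could hold both?** Treatment status is open to the sponsor (4.5), and the sponsor's laboratory is one reading site (6.2, 12.5). No limit by role or time is stated. No passage gives the list to individual readers.

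**3. When?** Assume all participants are treated within the planned 4 months of recruitment (4.9).
- Last participant treated: month 4. Last 3-month visit, then unmasking: 4 + 3 = month 7.
- First nodulectomy: month 18, so the gap is 18 − 7 = 11 months.
- Last nodulectomy: 4 + 18 = month 22, so the gap is 22 − 7 = 15 months.

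These gaps are before the visit windows (±14 days at month 3, ±60 days at month 18). On this timeline all reading follows unmasking.

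**4. The plan's own sample size (8.1), as a check on the inputs.** The rates are 30% and 15%, with two-sided alpha 0.05, power 80%, 6 female worms per person and ICC 0.30.
- Two-proportion formula without continuity correction: n = [1.96·√(2 × 0.225 × 0.775) + 0.8416·√(0.30 × 0.70 + 0.15 × 0.85)]² / 0.15² = 121 worms per arm, rounded up.
- Design effect: 1 + 0.30 × (6 − 1) = 2.5.
- Subjects: 121 × 2.5 / 6 = 50.4, rounded up to 51. The plan's 51 is reproduced.

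**5. Illustration of what a reading shift would do.** The shift sizes are assumptions; the documents give none.
- Effective worms per arm: 51 × 6 / 2.5 = 122.4.
- With 30% truly fertile in both arms, SE = √(2 × 0.3 × 0.7 / 122.4) = 0.0586.
- If the reconciled result in one arm moves by d, the rejection rate is P(|Z + d/SE| > 1.96).

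| Shift d in the reconciled reading | d/SE | False-positive rate |
|---|---|---|
| 0 | 0 | 5.0% |
| 1.5 points | 0.26 | 5.8% |
| 2.5 points | 0.43 | 7.1% |
| 3 points | 0.51 | 8.1% |
| 5 points | 0.85 | 13.7% |

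The 1.5 and 2.5 point rows are the cases where one of two readers shifts by 3 or 5 points and reconciliation splits the difference (also an assumption). Letting the variance follow the shifted rate gives the same 8.1% at 3 points, which is a 10% relative under-call of fertile worms.

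**The case against.** The strongest reply is that masking is specified. Readers get only the slide and its label, are stated to be masked, and work at two independent sites with separate entry and a third reader available. The immunostain makes the live/dead call less subjective. Treatment information is kept apart from the case report form (4.5), the database is password protected (11.6), and the data capture system has audit trails (9.4). A patient number means nothing to someone without the list.

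Most of this stands as mitigation. Slides are not read by the sponsor alone, and masked reading is not the only protection. But double reading and staining limit the effect of one reader's drift without hiding the arm, and the readers resolve discrepancies together. The database controls are general: they do not say that readers are shut out of assignments.

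A reader might infer that histologists at the sponsor's laboratory will know assignments, or that the primary result will be biased. The documents support neither. Access for the sponsor as an organisation is not access for each slide reader, and unmasking by the data manager serves the 3-month safety comparison. Nothing says that readers are told.

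A further objection is that the 3-month results cannot be confined to the DSMB, because section 8.3 owes an interim report to regulators and ethics committees. That is right, and the fix below does not require it.

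**Conclusion.** The plan lacks a safeguard. Its own labelling method and access rule leave the promise of masked reading open to linkage, for a judgement-based primary endpoint in an open-label trial. This is neither a demonstrated bias nor a broken mask.

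The conclusion rests on the patient number being the study ID, and on the planned timeline, which puts unmasking roughly 11 to 15 months before nodules are removed. The false-positive rates of about 8% and 14% are illustrations only. They require the reconciled reading to move by 3 or 5 points in one arm and not the other. If only one reader shifted and the difference were split, they fall to about 5.8% and 7.1%. Their use is to show that shifts of 3/15 = one fifth to 5/15 = one third of the planned 15-point effect would matter. The change is a cheap improvement that should be made before slides are read.

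**What to change.** Amend sections 4.5 and 6.2 as follows:
- Relabel nodule slides with random codes unrelated to the participant number, and mix arms across reading batches.
- Name a code-key holder outside both reading sites, who releases the key only after both reads and the reconciliation are locked.
- State that nodule readers at both sites, and the readers of the 12- and 18-month skin snips, have no access to individual assignments until that lock.

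By-arm safety summaries can still go into the 3-month interim report, since they need not disclose individual assignments. Section 4.5's provision for sharing treatment for medical purposes is unaffected.

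The cost is relabelling and chain-of-custody bookkeeping, with some risk of a labelling error that a double-checked code list would contain. No extra participants, readers or procedures are needed.

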Samples will be collected for later studies of biomarkers of *Onchocerca* infection. 5ml of peripheral venous blood and 10 ml of first void morning urine will be obtained prior to the Part II treatment and at 3, 12, and 18 months after treatment. Post-treatment samples will be compared with samples collected prior to the Part I IVM clearing dose and with samples collected just prior to treatment in this study (Part II). Samples will be stored at the UHAS study site until they are shipped to the USA for analysis (see paragraph 6.1). Analysis of samples will take place at the [name] Lab at Washington University in St. Louis. Samples will be stored for up to 35 years and then destroyed according to regulatory guidelines.

Parasitological Evaluations

Palpation for subcutaneous *Onchocerca* nodules: This baseline information will be available from the preceding related study, but nodule palpation will also be performed at the time of nodulectomy

Skin snip testing to detect microfilaria in skin

Skin snip testing for Mf will be performed at 3, 12 and 18 months. We will obtain four (4) skin snips using a corneoscleral punch. Each snip will be weighed on an analytical balance and incubated for at least 8 hours in isotonic saline in a well of a flat-bottomed micro-titre plate at ambient temperature. Microfilariae will be counted by microscopy. Mf number and skin snip weight will be recorded. The mean skin microfilarial density will be calculated and recorded as mf/mg. Skin snips will also be preserved for later PCR testing to detect parasite DNA (more sensitive than microscopy).

Nodulectomies

Nodulectomies will be performed at 18 months after IDA treatment. Nodules will be surgically excised by Ghanaian study medical officers, under local anesthesia (1% xylocaine) in a specially designated room at the University of Health and Allied Sciences School of Public Health Research Centre using aseptic procedures. At the final visit at 18 months post-treatment participants will be brought to the centre in Hohoe for 2 days for nodulectomies. After the procedure they will then be returned to their communities where a study nurse and will be stationed to continue wound management.

Wound treatment for Nodulectomy

Wound management will begin with the nodulectomy incision and continued till all wounds are healed. Subjects will usually be detained on the ward after surgery for two days or longer. During this period, wounds are examined for bleeding, hematoma formation and dehiscence. Subjects will be advised to stay off work for the first week post surgery to assist in wound healing. Compensation will be paid for loss of earnings for the seven (7) days if appropriate. The first change of dressing is done on the first day after nodulectomy. On day 10 post-nodulectomy, sutures will be removed. Subsequent dressing changes will occur on alternate days until wound is completely healed. Nurses will assist with wound care management in the community. This study draws participants from 5 communities, but at any one time there will only be participants from 1 or 2 communities who require care for nodulectomy wounds. Additionally, cohorts of participants receiving nodulectomies are staggered so that there are not more than 20 participants requiring wound care at one time. Two nurses will be available in the communities to monitor wound healing and provide wound management and dressing changes as needed.

Ocular Examinations:

The following **ocular examinations** will be performed by qualified medical personnel at the University of Health and Allied Sciences School of Public Health Research Centre in Hohoe:

1. Visual acuity exam: using a standard Snellen or E chart, individuals will stand or sit 20 feet (6 meters) from the chart with both eyes open. They will be asked to cover one eye with the palm of the hand (or a small paddle) and read out loud the smallest line of letters that can be seen. The test is done in each eye, one at a time.
2. Visual fields: We will assess visual fields either by confrontational testing and/or by automated VF perimetry testing. Both tests are widely used and non-invasive.
3. Pupillary reflex response testing: This will involve shining a light in one eye and then examining pupillary response and the degree of constriction in the illuminated pupil as well as consensual response, or the response in the opposite pupil. This test can suggest asymmetric optic nerve or retinal disease.
4. Applanation tonometry: this test measures intraocular pressure. We will apply local anesthetic drops approved for use in Ghana in each eye to numb the surface of the eye and then apply a fine fluorescein strip to tear film of each eye. The slit lamp is placed in front of the individual and the Goldmann tonometer will measure the intraocular pressure.
5. Slit lamp examination: using a slit lamp, we will evaluate each participant for Mf in the anterior chamber of eye (after having the subject position their face downwards for at least 2 minutes). We will look for the presence of anterior segment and posterior segment disease, including but not limited to uveitis, limbitis, cataracts, corneal scarring, optic nerve disease, and retinal disease. A 90 Diopter and 78 Diopter lens will be used in conjunction with the slit lamp to visualize the fundus (fundoscopy).
6. Indirect ophthalmoscopy: this fundoscopy examination technique will be optionally performed at the discretion of study ophthalmologists and optometrists to evaluate the fundus of the eye (posterior segment) particularly for suspected retinal detachment. Prior to the test, the examiner will apply eye drops approved for use in Ghana to dilate the pupil and then use the indirect ophthalmoscope to visualize the different structures in the posterior segment of the eye after the pupil is dilated.

7. Retinal photography: Flash photography of the retina and optic nerve will be taken to document anatomical findings. Black and white and color images will be recorded. Retinal photography will be taken with the pupils dilated. Pupils will already have been dilated for fundoscopy (see above), and therefore, retinal photography will not require re-dilation of the pupil. Faces will not be included in these photographs.
8. Slit-lamp Photography. Photography of the anterior chamber will be taken whenever possible to record presence of microfilariae and anterior segment findings. Short videos will also be taken to record microfilarial motility or immotility. This can be performed prior to dilation, and will not require re-dilation of the pupil. Faces will not be included in these photographs.
9. Optical coherence tomography (OCT): this is a non-invasive method that uses low intensity laser light to capture micrometer-resolution, three-dimensional images of both the anterior and posterior segment of eye. It can visualize the full thickness cross-section of cornea, conjunctiva, anterior chamber, iris and retina and optic nerve head. Prior to the test we will apply eye drops (1% tropicamide) to dilate the pupil, which will already have been dilated for fundoscopy. Then the subject will be positioned in front of the OCT scan, resting the head on a support to keep it motionless. The equipment scans the eyes without touching them. Scanning takes 5-10 minutes. Because this technology utilizes light waves, media opacities such as vitreous hemorrhages, dense cataracts or corneal opacities may interfere with an optimal imaging.

General health examination and skin evaluation.

Each participant will undergo a routine history and physical examination as part of the screening process for eligibility that will include vital signs, height, and weight. We will also collect history of any past and current medications with a focus on onchocerciasis related skin and/or eye disease and any prior treatment for onchocerciasis over the past 6 months

Skin evaluations will include a careful examination of the skin by a study physician; significant abnormalities (grade 2 or higher) present during the baseline examination will be documented by photography. Skin survey and records of baseline skin disease with photographs in persons with significant abnormalities will be collected in the case report form. **Faces will not be included in photographs.**

